- **AIS C; Motor Incomplete:** Motor function is preserved at the most caudal sacral segments for voluntary anal contraction OR the patient meets the criteria for sensory incomplete status (sensory function preserved at the most caudal sacral segments (S4 to S5) by light touch, pin prick, or deep anal pressure) and has some sparing of motor function more than 3 levels below the ipsilateral motor level on either side of the body (This includes key or non-key muscle functions to determine motor incomplete status). For AIS C – less than half of key muscle functions below the single neurological level of injury have a muscle grade ≥ 3 .
- **AIS D; Motor Incomplete:** Motor incomplete status as defined above, with at least half (half or more) of key muscle functions below the single neurological level of injury having a muscle grade ≥ 3 .
- **AIS E; Normal:** If sensation and motor function as tested with the ISNCSCI are graded as normal in all segments, and the patient has prior deficits, then the AIS grade is E. Someone without an SCI does not receive an AIS grade.

Using “Not Determined” (ND): To document the ASIA Impairment Scale grade when it is unable to be determined based on the examination results.

Conversion of 2 or more AIS grades has been used previously as a clinical assessment of significant neurologic recovery.^{47,48}

The motor level for the right or left side is defined by the lowest key muscle function that has a grade of at least 3 (on supine testing), provided the key muscle functions represented by

segments above that level are judged to be intact (graded as a 5). Note: In regions where there is no myotome to test, the motor level is presumed to be the same as the sensory level, if testable motor function above that level is also normal. The motor level is determined for both the right and left sides of the body; the right and left motor level may be different. For additional details, please see the ISNCSCI Scoresheet in Section 15.1. An improvement of 2 or more motor levels on either side has been shown to correlate with functional improvements.^{4,30}

[figure not shown]

Table 8-1 Summary of Efficacy Endpoints and Assessments

Efficacy Endpoint	Efficacy Assessment
Primary Endpoint	
Change from baseline in upper extremity motor score (UEMS) at 6 months after treatment	ISNCSCI examination
Secondary Endpoints	
Spinal Cord Independence Measure (SCIM) III Self-Care subscore at 6 months after treatment	SCIM III

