12.3.5 Interim and IDMC Analyses

12.3.5.1 Interim Analyses

An interim analysis will be conducted when 33% of enrolled patients have completed the 6-Month Follow-up Visit. Based on the results of this interim analysis, the study may continue or stop for futility. The IDMC will conduct review of this interim analysis and make recommendation to the sponsor. If the study is considered unsuccessful at the time of the interim analysis, the study is to be terminated, study enrollment is to be stopped, and subjects are to be followed for safety reasons only.

Vertex will conduct the primary analysis for the study that includes safety, efficacy, and PK after all subjects receiving study drug have completed the 6-Month Follow-up Visit, or Early Termination Visit/Safety Follow-up Visit for subjects who prematurely terminate from the study before the 6-Month Follow-up Visit, and all data from these visits have been entered into the clinical study database, and the data have been cleaned and locked. If the study is considered unsuccessful at this primary analysis, the study is to be terminated and subjects are to be followed for safety reasons only. If the study is considered successful at this analysis, an updated analysis will be conducted by Vertex after all subjects receiving study drug have completed the 12-Month Follow-up Visit, or Early Termination Visit/Safety Follow-up Visit for subjects who prematurely terminate from the study before the 12-Month Follow-up Visit, and all data from these visits have been entered into the clinical study database, and the data have been cleaned and locked.

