7.2 Sample Size and Power

The primary efficacy endpoint is the change from baseline in UEMS at 6 months after treatment.

The null hypothesis to be tested is that the mean change from baseline in UEMS at 6 months after treatment is the same for 9-mg dose of VX-210 and placebo. This null hypothesis will be tested at 2-sided significance level $\alpha = 0.05$.

The sample size was calculated using a projected standard deviation (SD) of 6.0, based on the variability of improvement in UEMS scores of cervical subjects in the historical Sygen database. Anticipated withdrawal of 10% of subjects before the first follow-up assessment was also included in the sample size calculation.

If 9-mg dose group improves in UEMS by 4 points over placebo (a clinically meaningful increase), a total of approximately 100 subjects (approximately 50 per arm) will have approximately 82.1% power to detect a statistically significant treatment effect for 9-mg dose group compared to placebo, considering the interim futility analysis.

Based on the review of data from Anderson et al., the SD was projected to be 3.8 for SCIM III Self-Care subscore. [Table 7-1](#) presents the estimated power for detecting various

treatment differences between an active treatment group and the placebo group in SCIM III Self-Care subscore, assuming 45 randomized subjects with follow-up assessment in each treatment group without considering the possible power loss from the interim futility analysis.

Table 7-1 Power Estimates Under a Variety of Treatment Differences, Given 45 Randomized Subjects With Follow-up Assessments in Each Treatment Group

Mean Difference in SCIM III Self-Care Subscore	Power (%)
1	23
2	69
3	95

Power estimates are based on 2-sided t-test with $\alpha = 0.05$.

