9 STATISTICAL ANALYSIS

9.1 General Considerations

The Schedule of Assessments is provided in [Appendix A](#).

The precision standards for reporting safety and efficacy variables are provided in an internal Biometrics document that specifies the programming rules, including the precision for derived variables.

All individual subject data for subjects who were randomized or received study drug will be presented in individual subject data listings.

Continuous variables will be summarized using the following descriptive summary statistics: the number of subjects (n), mean, SD, standard error (SE), median, minimum value (min), and maximum value (max).

Categorical variables will be summarized using counts and percentages. Percentages will be presented to 1 decimal place unless otherwise specified.

Baseline value, unless otherwise specified, will be defined as the most recent non-missing measurement (scheduled or unscheduled) collected before administration of study drug.

Change (absolute change) from baseline will be calculated as:

Post baseline value - baseline value.

The treatment-emergent (TE) period will include the time from dosing with study drug to the Safety Follow-up Visit or 28 days after treatment / the last available visit (whichever is later) for subjects who do not have a Safety Follow-up Visit.

Unscheduled visits: Unscheduled visit measurements will be included in analysis as follows:

- In scheduled visit windows per specified visit windowing rules.
- In the derivation of baseline measurements
- In the derivation of maximum/minimum values and maximum/minimum changes from baseline values.
- In individual subject data listings as appropriate.

Visit window rules: The analysis visit windows for protocol-defined visits are provided in [Appendix B](#).

Repeated observations within the same visit window:

- For all efficacy parameters, if there are multiple measurements within a visit window, the record at the scheduled visit will be used. If there are no measurements at the scheduled visit, then 1) the record closest to the target day will be used; or 2) if there are multiple records with the same distance to the target day, the latest record will be used.
- For all safety parameters, if there are multiple measurements within a visit window, then 1) the record closest to the target day will be used; or 2) if there are multiple records with the same distance to the target day, the latest record will be used.

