9.3 Efficacy Analysis

Assessment of efficacy of VX-210 treatment is one of the primary objectives of this pivotal study. All efficacy endpoints will be analyzed based on the FAS. All Efficacy data will be presented in listings based on the All Subjects Set.

The primary efficacy analysis in this study targets an estimand that would assess efficacy by using the change from baseline in the UEMS score at 6 months after treatment, focusing on the effect attributable to the initially randomized treatment.

Such an estimand targets the effect of the initially randomized treatment regimen, with consideration for the fact that enrolled subjects will also receive standard of care. With such

an estimand, all subjects in FAS with their primary efficacy endpoint data collected at 6 weeks, 3 months, 6 months, and 12 months after treatment are used to assess the targeted treatment effect. The primary efficacy analysis will be based on a mixed-effects model for repeated measures (MMRM), estimated using restricted maximum likelihood, treating the change from baseline in the UEMS score at 6 weeks, 3 months, 6 months, and 12 months after treatment as the dependent variable. If change from baseline in the UEMS score is missing after the visit windows rules have been applied, the missing value will be assumed to be Missing At Random (MAR) conditional on the observed data. With use of the MMRM model and the MAR assumption, no missing data will be explicitly imputed.

[REDACTED]

The primary result obtained from the primary efficacy analysis will be the estimated mean treatment effect at 6 months after treatment, and the estimated mean treatment effects at 6 weeks, 3 months, and 12 months after treatment, obtained from the model established, will also be provided.

[REDACTED]

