- Motor level change from baseline at 6 months after treatment: A motor level responder is defined as a subject with improvement by ≥ 2 motor levels on either side of the body (i.e., baseline level C4 changed to C6, C7, C8 on the left; or baseline level C5 changed to C7, C8... on the right and so on). A subject with a missing/not determined motor level on one side of the body for a given visit and an improvement of ≥ 2 motor levels on the other side of the body at that visit will be classified as a responder for that visit; for all other cases in which one or both motor levels are missing/not determined at a given visit, the responder result at that visit will be noted as 'missing'. The motor level at baseline, 6 weeks, 3 months, 6 months, and 12 months after treatment will be summarized descriptively by treatment group. The motor level responder, defined as aforementioned, at 6 weeks, 3 months, 6 months, and 12 months after treatment will also be summarized descriptively by treatment group.

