10 SUMMARY OF INTERIM AND IDMC ANALYSES

10.1 Interim Analysis

An interim analysis will be conducted when approximately 33% of enrolled subjects have completed the 6-month follow-up visit. Based on the results of this interim analysis, the study may continue or stop for futility. The IDMC will conduct review of this interim analysis and make recommendation to the sponsor. If the study is considered unsuccessful at the time of the interim analysis, the study is to be terminated, study enrollment is to be stopped, and subjects are to be followed for safety reasons only.

Based on the review of the data provided at the interim analysis meeting, the IDMC will make a recommendation regarding whether the study should continue or should stop for futility. The guideline for futility stopping will be that the 9-mg dose group improves in UEMS by less than approximately 1.19 points over placebo for the approximately 33% of subjects analyzed, under the assumed standard deviation (SD) of 6.

The IDMC will review the observed SD at the time of the interim analysis. If the SD deviates from the assumption, the futility guide is adjusted to be that the study will be stopped for futility if conditional power (under observed primary endpoint treatment effect size) is <10.6% or the observed primary endpoint treatment effect size is <1.19. The following table presents examples of the futility boundary with respect to different sizes of SD. The last column refers to the minimum observed primary endpoint effect size that is required to achieve statistical significance under the given size of SD at the final analysis.

Table 10-1 Guidelines for Futility Stopping

Standard Deviation	Futility Boundary	Conditional Power (Under	Minimum Required Observed
---------------------------	--------------------------	---------------------------------	----------------------------------

		Observed Effect Size)	Effect Size at Final Analysis
4	1.19	25.1%	1.7
6	1.19	10.6%	2.5
8	1.59	10.6%	3.3
10	1.98	10.6%	4.1

In all analyses supporting this interim analysis, only the first 43 randomized subjects will be used unless otherwise specified; this sub-population includes approximately 33% of enrolled subjects who are dosed with placebo or 9-mg of VX-210 and who will have completed the 6-month follow-up visit at the time of the interim analysis data cut.

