- **GRASSP Quantitative Prehension score at 6 months after treatment:** The GRASSP Quantitative Prehension score at 6 months after treatment will be summarized descriptively by treatment group. The ANCOVA analysis of the GRASSP Quantitative Prehension score at 6 months after treatment is similar to the ANCOVA analysis of the SCIM III self-care subscore at 6 months after treatment in the interim analysis except for that the relevant endpoint here is the GRASSP Quantitative Prehension score at 6 months after treatment.
- **AIS grade conversion from baseline at 6 months after treatment:** The definition of an AIS responder is same as that in the primary analysis (see section 9.3.2.1). The AIS grade at baseline, 6 weeks, 3 months, 6 months, and 12 months after treatment will be summarized descriptively by treatment group. The AIS responder at 6 weeks, 3 months, 6 months, and 12 months after treatment will also be summarized descriptively by treatment group.
- **Motor level change from baseline at 6 months after treatment:** The definition of a motor level is same as that in the primary analysis (see section 9.3.2.1). The motor level at baseline, 6 weeks, 3 months, 6 months, and 12 months after treatment will be summarized descriptively by treatment group. The motor level responder at 6 weeks, 3 months, 6 months, and 12 months after treatment will also be summarized descriptively by treatment group.

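### Does the SAP have to say whether motor-level responder results noted as missing stay in the percentage denominator?

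*SAP*

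**What the plan says.** SAP 9.3.2.1 defines the motor-level responder as a gain of two or more levels on either side. With one side undetermined, a sufficient gain on the other side still makes a responder. Otherwise, when "one or both motor levels are missing/not determined at a given visit, the responder result at that visit will be noted as" missing. The responder is then summarized descriptively by arm at each follow-up visit.

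Two general rules apply. SAP 9.1: "Categorical variables will be summarized using counts and percentages". SAP 9.3: "All efficacy endpoints will be analyzed based on the FAS", with all efficacy data also presented in listings. Neither says what a percentage is taken over when a result is missing. SAP 9.2.1, by contrast, names the FAS as the base for disposition percentages. The carry-forward rule in SAP 9.1 covers SCIM III Self-Care, CUE-T and GRASSP only.

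On timing, SAP 10.1 places the interim at about 33% of enrolled subjects with the 6-month visit. If the study is then judged unsuccessful, "the study is to be terminated, study enrollment is to be stopped, and subjects are to be followed for safety reasons only". SAP 10.1.2 nevertheless tabulates 12-month results at the interim: "The motor level responder at 6 weeks, 3 months, 6 months, and 12 months after treatment will also be summarized". Protocol 12.3.5.1 holds the primary analysis until "after all subjects receiving study drug have completed the 6-Month Follow-up Visit", or have had an Early Termination or Safety Follow-up Visit.

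**The concern.** Missing here covers two different things: an examination that left a side undetermined, and no examination at all. The first should be uncommon. The second could be common in a 12-month table produced at a 6-month cut, or after a futility stop that leaves subjects followed for safety only.

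The coding is also asymmetric. A subject with one undetermined side can be a responder or missing, but never a non-responder. Dropping missing results therefore pushes the rate up, while keeping them in the denominator pulls it down. If the choice is made after the data are seen, a named secondary endpoint could be shown at quite different sizes. The AIS responder raises the same question: Protocol 8.2.3.2 provides a Not Determined code ("To document the ASIA Impairment Scale grade when it is unable to be determined based on the examination results"), and the visible SAP gives no rule for it.

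**Working it through.** The documents give no figure for this endpoint, so there is nothing of the plan's own to reproduce for it.

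**Inputs**
- From the plan: about 50 subjects per arm (SAP 7.1); "Anticipated withdrawal of 10% of subjects before the first follow-up assessment" (SAP 7.2), so 50 × 0.90 = 45 per arm followed.
- Assumed: true either-side response p = 0.30; per-side response s = 0.20; share of examined subjects with one side undetermined m = 0.10; absence of an examination unrelated to outcome. V is the share of the FAS examined.

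**Formulas**
- Responders per examined subject: (1−m)p + ms = 0.27 + 0.02 = 0.290.
- Classifiable results per examined subject: (1−m) + ms = 0.90 + 0.02 = 0.920.
- Missing excluded: 0.290/0.920 = 31.5%, whatever V is.
- Missing kept (FAS denominator): 0.290 × V.

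| V | Excluded | FAS | Gap (points) |
|---|---|---|---|
| 100% | 31.5% | 29.0% | 2.5 |
| 90% | 31.5% | 26.1% | 5.4 |
| 67% | 31.5% | 19.3% | 12.2 |
| 50% | 31.5% | 14.5% | 17.0 |
| 33% | 31.5% | 9.7% | 21.9 |

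Gaps are taken before rounding.

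**Sensitivity at V = 90%.** With m = 0: 30.0% against 27.0%, a gap of 3.0. With m = 0.20: 0.28/0.84 = 33.3% against 0.28 × 0.9 = 25.2%, a gap of 8.1.

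**Arm difference.** Take p = 0.45, s = 0.30 on drug against 0.30, 0.20 on placebo, with m = 0.10. Drug: 0.405 + 0.030 = 0.435 responders and 0.90 + 0.03 = 0.93 classifiable, so 46.8% with missing excluded.
- Excluded: 46.8 − 31.5 = 15.3 points.
- FAS, V = 90%: 39.15 − 26.1 = 13.05 points.
- FAS, V = 50%: 21.75 − 14.5 = 7.25 points.

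The true difference is 15 points. At V = 90% the choice moves the estimate by about 2.2 points. For scale, the standard error of a difference between two 30% rates with 50 per arm is √(2 × 0.3 × 0.7/50) = 9.2 points.

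**Which rows apply**
1. The endpoint is at 6 months, and the primary analysis waits for that visit or early termination. In a study that runs on, the 90–100% rows apply.
2. ISNCSCI is scheduled at the Early Termination Visit (Protocol Table 3-1), which is held on withdrawal or site closure (Protocol 8.1.4). SAP Appendix B accepts days 137 to 273 as the 6-month visit, so some of these examinations fill the window.
3. SAP section 4 says the interim methods of Version 1.0 have already been carried out. New wording cannot alter tables already produced.
4. The lower rows apply to 12-month tables at a 6-month cut, or to 6- and 12-month tables after a stop that ends the examinations. If the study succeeds, Protocol 12.3.5.1 adds an updated analysis after 12-month completion.

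**The case for a change.** The strongest reply is that a stop is no remote case. With 15 per arm at the interim and SD 6, the chance of falling below the 1.19-point futility boundary is Φ(1.19/(6√(2/15))) = Φ(0.54) = 71% if the drug does nothing. It is Φ((1.19 − 4)/2.19) = 10% at the planned 4-point effect. Heavy missingness is thus foreseeable from the plan's own rules, and the large gaps could reach the 6-month table. The documents do not report the interim's outcome. Unequal missingness can also create a false difference over the FAS: 18 of 45 and 14 of 35 are both 40% of those observed, but 36% and 28% of 50, an 8-point difference from nothing. Finally, Protocol 12.3.3.2 names a stratified Cochran-Mantel-Haenszel test for this endpoint.

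The arithmetic stands, and so does the observation that the denominator is unstated. It does not make the plan wrong. After a futility stop, the percentage describes a study already judged on UEMS. The false-difference example argues against a bare FAS percentage, so a rule fixing the FAS denominator would need the number examined, and a split of the missing row, to avoid misleading. Responders over the observed number, with the missing count shown, would serve equally well. As for the test, the visible SAP analysis of this endpoint is descriptive, SAP 9.3.4 marks multiplicity adjustment as not applicable, and the two endpoints that Protocol 12.3.3.4 names in the hierarchy are UEMS and SCIM III Self-Care.

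**Conclusion.** The visible SAP leaves the denominator open, but this is missing reporting detail and needs no change. No stated rule gives a wrong result. A FAS table with a row for missing is the ordinary reading of SAP 9.1, 9.3 and 9.3.2.1 together, and the listings let a reader form either rate. The redacted blocks in SAP 9.3, or the internal programming document mentioned in SAP 9.1, may already settle it; neither can be seen.

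For the 6-month endpoint in a study that runs on, the choice moves the descriptive rate by about 2.5 to 5.4 points (3.0 to 8.1 at 90% examined as one-side gaps run from 0 to 20%). The 12- to 22-point gaps are confined to 12-month tables at a 6-month cut or to tables after a stop. All these sizes rest on assumed response and gap rates. Type I error, power and the futility rule are untouched. The AIS responder is also summarized descriptively, so the same conclusion holds there.

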9.3.4 Multiplicity Adjustment

Not applicable.

9.4 Safety Analysis

All safety summaries will be based on the set of data associated with the TE period for subjects in the Safety Set.

The overall safety profile of VX-210 will be assessed in terms of the following safety and tolerability endpoints:

- Incidence of treatment-emergent adverse events (TEAEs)
- Clinical laboratory values (i.e., hematology, serum chemistry, coagulation studies, and urinalysis)
- ECGs
- Vital signs

All safety data will be presented in individual subject data listings.

9.4.1 Adverse Events

For analysis purposes, AEs will be classified as pretreatment AEs, TEAEs, or post-treatment AEs, defined as follows:

- Pretreatment AE: Any AE that started prior to dosing with study drug.
- TEAE: Any AE that developed or worsened at or after dosing of study drug through the end of the TE period.
- Post-treatment AE: Any AE that developed or worsened beyond the TE period.

For AEs with missing or partial missing start dates, if there is no clear evidence that the AEs started before or after study treatment, then the AEs will be classified as pre-treatment AEs/TEAEs/post-treatment AEs. Imputation rules for missing or partial AE start date are defined in the [Appendix D](#).

AE summary tables will be presented for TEAEs only, overall and by treatment group, and will include the following:

- All TEAEs
- TEAEs by relationship
- TEAEs by maximal severity
- Serious TEAEs

- TEAEs leading to death

Summaries will be presented by MedDRA system organ class and preferred term using frequency counts and percentages (i.e., number and percentage of subjects with an event as well as total number of events). When summarizing the number and percentage of subjects with an event, subjects with multiple occurrences of the same AE or a continuing AE will be counted once, only the maximum severity level will be presented in the severity summaries, and the worst/highest relationship level in the relationship summaries.

An AE overview table will be provided.

A listing containing individual subject AE data for all deaths and other serious AEs will be provided separately. All AEs, including pre- and post-treatment AEs, will be presented in individual subject data listings.

